12.2 Statistical analysis

A separate Statistical Analysis Plan will provide a detailed description of the planned analyses. A brief outline is given below.

Point estimates, 95% confidence intervals and p-values from two-sided tests will be calculated for all main outcome measures. Outcome will be adjusted for the minimisation variables. Analysis will be of all randomised subjects in the intention to treat population.

12.2.1 Primary Outcome Analysis

The primary endpoint is the effect on CS rate of high does regimen versus standard dose regimen oxytocin. A log-binomial regression model to calculate the relative risk and 95% confidence of the primary outcome. Centre and degree of dilation at recruitment will be included as covariates. The p-value from the associated chi-squared test will be produced and used to determine statistical significance.

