7.2 Setting

Delivery Suite of approximately 30 Maternity Units within the UK.

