7.8 Co-enrolment

Women participating in the HOLDS study cannot join other interventional trials of an IMP or procedure for delay in labour. They may be recruited to other intrapartum IMP studies. Women may be recruited to non-interventional trials such as observational or qualitative studies for delay in labour and to all other trials in pregnancy or the postnatal period.

8 Randomisation

Randomisation will be by telephone via an automated secure system developed by the Health Services Research Unit at Aberdeen University. Eligibility will be confirmed as part of the recruitment process and checked by the automated telephone randomisation system. Although some identifiable data is provided it is insufficient to constitute personal identifiable data.

Randomisation will be available 24 hours a day. Participants will be randomised at the level of the individual in a 1:1 ratio to either standard dose regimen oxytocin or high dose regimen oxytocin. A minimisation algorithm will be used to ensure balance in the allocation over the following variables:

- degree of cervical dilation in cm (<6/>=6);
- age in years (<20/>=20 to <30/>=30 to <40/>=40);
- maternity unit

A 'random element' will be included in the minimisation algorithm so that each patient has a probability (unspecified here) of being randomised to the opposite treatment that they would have otherwise received.

Resupply of subsequent treatments, should they be required, will be by the same secure system to guarantee allocation to the same dose as initial randomisation.

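### Maternal age is a minimisation variable, but the primary model in 12.2.1 leaves it out while 12.2 calls for adjustment for the minimisation variables, so the primary covariate set is not uniquely fixed

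*Combined protocol and SAP*

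**What the plan says.** Section 8 (Randomisation) names three minimisation variables: "degree of cervical dilation in cm (<6/>=6" (two levels), "age in years (<20/>=20 to <30/>=30 to <40/>=40" (four bands) and "maternity unit". Section 7.2 puts the number of units at about 30.

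Section 12.2 gives a general rule without exceptions: "Outcome will be adjusted for the minimisation variables".

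Section 12.2.1 specifies the primary analysis as follows: "A log-binomial regression model to calculate the relative risk and 95% confidence of the primary outcome". It continues: "Centre and degree of dilation at recruitment will be included as covariates". The decision rule is: "The p-value from the associated chi-squared test will be produced and used to determine statistical significance".

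Section 12.2.2 applies the primary method to the dichotomous secondary outcomes, with vaginal birth and tachysystole as its examples. Section 12.2 describes itself as a summary and leaves detail to a separate SAP. The supplied document contains no separate SAP text that settles the covariates.

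**The concern.** The general rule in 12.2 gives a primary model with three adjustment factors. The specific rule in 12.2.1 gives one with two. Nothing says which prevails or why age would be dropped, so an analyst could fit either model and cite the protocol.

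What is at stake is pre-specification of the one confirmatory test. If the two models fall on either side of 0.05, the choice could be made after the data are seen. The same gap passes to the dichotomous secondary outcomes, including a safety outcome, tachysystole. There is also an argument of principle: a factor used to force balance between the arms belongs in the analysis, because otherwise the reported standard error can be larger than the true variability of the estimate.

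**Working it through.** **1. The sections side by side**

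| Minimisation variable (Section 8) | Adjusted for under 12.2 | Named in 12.2.1 |
|---|---|---|
| Cervical dilation, <6/>=6 cm | yes | yes |
| Maternity unit | yes | yes, as centre |
| Age, four bands | yes | no |

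Two of the three variables are in the stated primary model. Only age is missing.

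**2. The plan's own sample-size figures (Section 12.1)**

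Use the pooled-variance formula for two proportions, two-sided alpha 0.05, 1:1 allocation, no continuity correction:

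n per arm = [1.960 × √(2p̄(1−p̄)) + z_β × √(p1(1−p1) + p2(1−p2))]² / (p1 − p2)²

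- 32% v 24%, 90% power: p̄ = 0.28, so n = [1.960 × √0.4032 + 1.282 × √0.4000]² / 0.08² = 660 per arm, 1320 in total. This matches the plan.
- 24% v 18%, 750 per arm: z_β = (0.06 × √750 − 1.960 × √0.3318) / √0.3300 = 0.895, giving power of 81.5%. The plan says 80%.

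The formula uses no covariates, so neither figure depends on whether age is in the model.

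**3. What adding age does**

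The documents give no age effect on caesarean section, no age mix, no between-unit variation and no value for the random element of the minimisation. All of these had to be assumed. Two simulations used 1,500 women, 30 units, a control rate of 24% and, for power, a relative risk of 0.75, with women assigned to the preferred arm with probability 0.8. Neither fitted the planned log-binomial model itself.

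Simulation A used linear risk-difference models with robust standard errors as a fast stand-in. The assumed age mix was 8/45/42/5%. There were 1,500 replicates under no treatment effect and 800 for power.

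| Assumed age relative risks | Mean SE without → with age (no treatment effect) | Type I error without → with age | Power without → with age |
|---|---|---|---|
| 1, 1, 1, 1 | 0.0218 → 0.0218 | 5.1% → 5.1% | 82.1% → 82.0% |
| 0.6, 1, 1.3, 1.8 | 0.0218 → 0.0216 | 4.5% → 4.7% | 81.6% → 82.3% |
| 0.4, 0.9, 1.5, 2.5 | 0.0218 → 0.0213 | 5.1% → 5.7% | 81.1% → 81.8% |

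The largest fall in the SE is 1 − 0.02126/0.02180 = 2.5%.

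Simulation B used modified Poisson regression with robust standard errors and 500 replicates per cell.

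- Age relative risks 0.5 to 2.0: power 85.0% without age and 86.4% with it, a gain of 1.4 points. Type I error was 3.0% and 4.0%.
- Age relative risks 0.6 to 1.8: power 83.8% and 84.2%, a gain of 0.4 points.

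Across both simulations, power changes by −0.1 to +1.4 points.

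**4. Is the test without age conservative?**

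In simulation B the Monte Carlo standard error of a type I error rate is about √(0.04 × 0.96/500) = 0.9 points, so 3.0% against 4.0% is not a usable contrast. In simulation A it is √(0.05 × 0.95/1500) = 0.6 points, and the model without age gives 4.5% to 5.1%, which is nominal. Under the strongest age effect in A, the mean SE without age (0.0218) equals the actual scatter of the estimates (0.0218), so the SE is not visibly too large.

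**5. How often the choice would matter**

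A further run of the same linear type, again on assumed inputs, counted how often the two covariate sets disagreed on p < 0.05. They did so in 0.1% to 1.6% of simulated trials.

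**The case against.** The strongest defence is that Section 12.2 is only a summary, that detail is left to a separate SAP, and that 12.2.1 does not present its two covariates as a complete list. On that view the general rule supplies age and 12.2.1 is merely incomplete. This is a fair account of how the text may have arisen. It does not settle the matter: summary status excuses missing detail, but here a named list for the confirmatory model differs from the rule a few lines above it. A SAP that is not in the supplied document cannot be relied on to resolve that.

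The second objection, that the numerical effect is small, stands in full.

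A reader might also infer stronger things that the documents and calculations do not support:

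- **That the stated model ignores the randomisation.** It keeps unit and dilation; the gap is age only.
- **That omitting age makes the test conservative or wastes material power.** The simulations do not show this reliably.
- **That adding age always helps.** If age is unrelated to caesarean section, the gain is nil (82.1% against 82.0%).
- **That significance may rest on an unadjusted 2×2 chi-squared test.** The sentence on the chi-squared test directly follows the model and its covariates, and 12.2 calls for adjustment. The natural reading is therefore the test of the treatment term in the adjusted model. Saying so is a clarification, not the repair of an error.

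The last objection concerns the fix. Log-binomial models can fail to converge, and adding terms does not help. With 30 units the stated model has an intercept, treatment, 29 unit terms and one dilation term: 32 parameters. Age makes it 35. At 24% v 18%, the expected number of caesareans is 750 × 0.24 + 750 × 0.18 = 315, or about 10 per unit, and the youngest and oldest age bands may be sparse. This part stands and is met by naming a fallback.

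**Conclusion.** The inconsistency between Sections 8, 12.2 and 12.2.1 is real and can be seen from the text alone. Age is left out of the primary model without explanation, so the covariate set for the primary outcome, and through 12.2.2 for the dichotomous secondary outcomes, is not uniquely pre-specified.

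The case for correcting it rests on pre-specification and on matching the analysis to the allocation scheme, not on power or error control. Validity is not threatened on the evidence here. The choice would rarely alter the conclusion, but where it did the primary result would be borderline. The sizes depend on the assumed age effects, age mix, unit variation and minimisation probability, and on stand-ins for the log-binomial model. The textual finding depends on none of these.

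**What to change.** In 12.2.1, replace the covariate sentence with wording to this effect: the model will adjust for all minimisation variables, namely maternity unit, cervical dilation (<6/>=6 cm) and age in the four minimisation bands. For clarity, add that the p-value for significance is the chi-squared test (Wald or likelihood-ratio, naming one) of the treatment term in that adjusted model. Because 12.2.2 refers back to the primary analysis, the dichotomous secondary outcomes follow. If age is left out on purpose, give the reason and amend 12.2 instead.

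State also how the units enter the model, and pre-specify a fallback if the log-binomial model does not converge, for example modified Poisson regression with robust standard errors.

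The cost is a few lines in the protocol and SAP, to be settled before unblinding, and three extra indicator terms. No new data are needed and the sample size is unaffected.

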12.2.2 Secondary Outcome Analysis

Dichotomous secondary outcomes (e.g. vaginal birth, tachysystole) will be analysed in the same fashion as the primary outcome. Time from randomisation to birth will be analysed by log-rank test with a Cox Proportional Hazard (PH) model also built if the assumptions of proportionality are met. Standard methods will be used to analyse other outcomes. Appropriate summary statistics split by group will be presented for each outcome (e.g. proportions/percentages, mean/standard deviation or median/interquartile range).

12.2.3 Missing Data/Sensitivity Analyses

Every attempt will be made to collect full follow-up data on all women (unless a woman withdraws consent for follow-up data collection). In particular, participants will continue to be followed-up even after any protocol treatment deviation or violation. It is thus anticipated that missing data will be minimal. Participants with missing primary outcome data will not be included in the primary analysis. This presents a risk of bias, and secondary sensitivity analyses will be undertaken to assess the possible impact of the risk. This will include a worse-case assumption that those women missing the primary outcome had a caesarean section. Other sensitivity analyses will involve simulating missing responses using a multiple imputation (MI) approach.

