6.1 Aim

HOLDS will provide robust evidence of clinical effectiveness of a high dose compared to the current standard dose regimen of oxytocin in reducing the need for Caesarean section (CS) for nulliparous women with confirmed delay in the first stage of labour.

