8.7 Withdrawal of trial/treatment or protocol violation

If a woman decides, after randomisation, she does not wish to be part of the trial, or there is a protocol violation, she will be withdrawn from the trial and will receive the standard dose oxytocin regimen using non- trial treatment. The timing of randomisation is as close as possible to the commencement of treatment so this should minimise the number of post-randomisation withdrawals or violations. The dose of oxytocin is titrated against uterine activity and the fetal heart rate, so it may be temporarily stopped and re-started as described in Section 8.3 above. Clear distinction will be made as to whether a participant is withdrawing from the trial but will still be followed up on an intention-to-treat basis, or whether the participant refuses any follow-up. If a participant explicitly withdraws consent to have any further data recorded their decision will be respected and recorded. All communication surrounding the withdrawal will be noted in the woman's hospital records and trial database, and no further data will be collected for that woman. If an SAE has occurred before her withdrawal we will follow this up to completion of the event.

Should a woman lose capacity to provide continued consent, they will be assumed to wish to remain in the HOLDS trial as there would be no further procedures or tests required for the trial.

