12.1 Sample size

The sample size is informed by the pilot study¹, recent survey of practice and Cochrane review⁶. The pilot study indicated a CS rate of 32% in the standard dose group (95%CI: 19% to 45%), whilst responses from the survey of practice (n=60 responses) indicate that a 25% relative reduction would be considered an important clinical difference to change practice. Detecting a difference of this size assuming a standard dose group rate of 32% (8% absolute reduction down to 24%) with 90% power (p=0.05) will require 1320 women. If the control group rate is lower, e.g. 24%, recruiting 1500 women would give 80% power to detect the same relative difference. We have selected the latter figure as our target sample size. The independent Data Monitoring Committee (DMC) will review the event rate to monitor the control rate on a six-monthly basis throughout the recruitment period.

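### The worse-case missing-data analysis in section 12.2.3 sets missing women in both arms to caesarean, which is not the worst case for the comparison unless every missing woman is on high dose

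*Combined protocol and SAP*

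**What the plan says.** Section 12.2.3 (Missing Data/Sensitivity Analyses) makes the primary analysis complete-case: "Participants with missing primary outcome data will not be included in the primary analysis". It accepts that this carries a risk of bias and plans secondary analyses to gauge it. The first is the one at issue: "This will include a worse-case assumption that those women missing the primary outcome had a caesarean section". The text draws no distinction between arms. The second is described only in outline: "Other sensitivity analyses will involve simulating missing responses using a multiple imputation (MI) approach". No departure from missing at random is stated for it. On quantity, the section says "It is thus anticipated that missing data will be minimal" and gives no figure.

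The outcome can be lost when a woman explicitly withdraws consent to further data. Section 8.7 then provides that "no further data will be collected for that woman".

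The effect measure is comparative. Section 12.2.1 specifies "A log-binomial regression model to calculate the relative risk and 95% confidence of the primary outcome", and section 6.1 sets the hoped-for direction as "reducing the need for Caesarean section (CS) for nulliparous women with confirmed delay in the first stage of labour", so benefit is an RR below 1 for high versus standard dose.

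**The concern.** Caesarean is the worse outcome for an individual woman, but the quantity under test is a ratio between arms. A caesarean assigned to a missing high-dose woman counts against high dose. One assigned to a missing standard-dose woman raises the comparator rate and counts in its favour. Applied to both arms, the rule partly cancels itself.

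At stake is how robust a positive result can be said to be. If the result holds under an analysis with this label, it may be described as surviving the worst case when that case was not examined. Multiple imputation as outlined does not supply a bound either.

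**Working it through.** **1. Inputs.** Section 12.1 gives two design scenarios: 32% v 24% caesarean (1320 women, 90% power), and 24% with the same 25% relative reduction, hence 18% (1500 women, 80% power). Allocation is 1:1 (section 8) and tests are two-sided (section 12.2). I use 750 per arm. The missing fractions are my assumptions.

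**2. The plan's own figures.** With p̄ the mean of the two rates, n per arm = [1.96√(2p̄(1−p̄)) + z_power√(pS(1−pS) + pH(1−pH))]² / (pS−pH)².
- 32% v 24% at 90% power: 659.9, so 660 per arm and 1320 in total, as stated.
- 24% v 18% with 750 per arm: power 81.5%, consistent with the stated 80%.

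**3. The two rules.** Let pH and pS be the rates among women with data (held at the design values) and fH and fS the missing fractions.
- High-dose rate with missing = CS: qH = pH(1−fH) + fH.
- Planned rule: RR_all = qH / [pS(1−fS) + fS].
- Least favourable to high dose: RR_ext = qH / [pS(1−fS)].
- RR_ext / RR_all = 1 + fS / [pS(1−fS)], which equals 1 only when fS = 0.

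So the planned rule is the worst case only when no standard-dose woman is missing.

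**4. When the planned rule enlarges the benefit.** RR_all is below pH/pS when fS/fH > [(1−pH)/pH] / [(1−pS)/pS].
- 24% v 18%: (0.82/0.18)/(0.76/0.24) = 4.556/3.167 = 1.44.
- 32% v 24%: (0.76/0.24)/(0.68/0.32) = 3.167/2.125 = 1.49.

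**5. Size with equal missingness.** Unadjusted RR; 95% CI = exp{ln RR ± 1.96√[(1−qH)/(750qH) + (1−qS)/(750qS)]}, where qS is the standard-dose rate under the rule. Example at 24% v 18%, 2% per arm: qH = 0.18×0.98 + 0.02 = 0.1964. Standard dose is 0.24×0.98 = 0.2352 with missing = no CS, or 0.2552 with missing = CS. Then 0.1964/0.2552 = 0.770 and 0.1964/0.2352 = 0.835.

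| Rates | Missing per arm | Planned, all CS | Opposite-arm extreme |
|---|---|---|---|
| 24% v 18% | 0.5% | 0.755 (0.621 to 0.919) | 0.771 (0.633 to 0.939) |
| 24% v 18% | 1% | 0.760 (0.626 to 0.923) | 0.792 (0.651 to 0.964) |
| 24% v 18% | 1.75% | 0.767 (0.634 to 0.928) | 0.824 (0.679 to 1.001) |
| 24% v 18% | 2% | 0.770 (0.637 to 0.930) | 0.835 (0.688 to 1.014) |
| 24% v 18% | 3% | 0.779 (0.647 to 0.937) | 0.879 (0.726 to 1.065) |
| 32% v 24% | 2% | 0.765 (0.653 to 0.897) | 0.814 (0.692 to 0.957) |
| 32% v 24% | 3% | 0.772 (0.661 to 0.902) | 0.847 (0.721 to 0.994) |
| 32% v 24% | 3.5% | 0.776 (0.664 to 0.905) | 0.863 (0.736 to 1.013) |

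The complete-case RR is 0.750 in every row.

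**6. Unequal missingness.** At 24% v 18% with 1% missing on high dose and 3% on standard dose, qH = 0.18×0.99 + 0.01 = 0.1882. The standard-dose rate is 0.24×0.97 + 0.03 = 0.2628 with missing = CS, or 0.2328 with missing = no CS. The planned rule gives 0.1882/0.2628 = 0.716, more favourable than 0.750. The opposite-arm extreme gives 0.1882/0.2328 = 0.808 (0.664 to 0.985), still significant. That pattern is about 8 v 22 women. If missingness were equally likely in the two arms, a split of 30 at least this uneven has two-sided binomial probability of about 0.016.

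**The case against.** The strongest reply is that little data should be missing. Mode of birth is known within the same admission. Section 11.1 describes primary outcome data as objective, routinely collected and transcribed from the records. Section 12.2.3 continues follow-up after deviations, and section 8.7 places randomisation close to treatment to limit withdrawals. Allocation is double blind (section 7.6) and care pathways are identical (section 8.3), so a large imbalance in missingness is unlikely. All of this stands, and it limits the practical weight of the point.

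It can also be said that the label means the worse outcome for the woman and claims no bound on the comparison, that the analysis is secondary, and that section 12.2 is an outline with detail deferred to a separate SAP. That SAP is not in the supplied text, so its content cannot be judged either way. But the stated purpose of these analyses is to assess bias in a comparison between arms, and nothing in the supplied text bounds that bias by arm.

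Two stronger readings are tempting. A reader might infer that the planned rule will generally flatter high dose. The documents do not support this: with balanced missingness it moves the RR toward 1, and they give no reason to expect more loss on standard dose. A reader might also infer that a positive result would fall under a proper worst case. That depends on a missing fraction the plan does not state, and at the main 32% v 24% design the extreme remains significant at 3% per arm.

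**Conclusion.** The point holds as a mis-specified and mislabelled sensitivity analysis; it is not a flaw in the primary analysis. That the rule is not the worst case follows from algebra and needs no assumption about quantity, beyond at least one missing woman on standard dose.

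The size depends on the assumed missingness. From 0.5% to 3% per arm at 24% v 18%, the planned rule stays between 0.755 and 0.779 and is significant throughout, while the opposite-arm extreme runs from 0.771 to 0.879 and loses significance from about 1.75%. At 32% v 24% it is lost at about 3.5%. At about 1% per arm or less, the two rules are unlikely to lead to different conclusions. These figures assume 750 per arm, observed rates equal to the design rates, and no covariate adjustment.

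**What to change.** In section 12.2.3, and in the separate SAP, add two arm-specific extreme-case analyses: (a) missing high dose = CS and missing standard dose = no CS; (b) the reverse. Keep the multiple imputation analysis. The existing analysis may stay, relabelled as all missing = CS.

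The cost is a sentence or two of text and one or two extra model runs, with no effect on conduct or sample size. The downside is wider and less favourable bounds, which should be reported as extremes that are implausible under blinding.

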12.2.4 Subgroup Analyses

Subgroup analyses will be limited to degree of cervical dilation at recruitment (<=6m/>6cm). Tests for statistical heterogeneity will be performed prior to any examination of effect estimates with subgroups. The results of subgroup analyses will be treated with caution and used for the purposes of hypothesis generation only.

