5.2 Additional relevant evidence

In the USA the Consortium of Safe Labor have recently published data that suggests that duration of labour appears longer today than in the past¹⁰ and that a cervical dilation of 6 cm appears to be a better marker for the start of the active phase of labour. This has been adopted by the American College of Obstetricians and Gynecologists with the Society for Maternal-Fetal Medicine in their consensus statement for 'Safe Prevention of Primary Caesarean Section'¹¹ as part of a number of strategies designed to reduce the caesarean section rate. In this statement they suggest that intervention for delayed labour should not start until the cervix is more than 6cms dilated and it is not clear what the standard oxytocin dose regimen should be. Using the data collected as part of the work undertaken by the Consortium of Safe Labor, an observational study¹² found no difference in CS rates with a so-called high dose oxytocin compared to a low dose. However, this study is open to methodological biases, the exact oxytocin dose regimens are unclear and, as they are presented within the paper, all the regimens would be considered standard dose regimens in the UK. Uptake of this evidence and the Consensus Statement¹¹ has been controversial in the USA¹³ and is unlikely to influence practice in the UK¹⁴. To ensure that the trial results will be of worldwide interest and relevance we will incorporate subgroup analysis of women commencing treatment less than 6cm and equal to or more than 6cm into our *a priori* statistical analysis plan.

6 Trial aim and objectives

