6.3 Secondary objectives

- To assess the effect on maternal and neonatal outcomes.
- To explore any variation in effect in women randomised with cervical dilation <6cms and >=6cms.
- To assess the safety of high dose oxytocin. Oxytocin can cause excess contractions (tachysystole) which can lead to abnormalities of the fetal heart rate (hyperstimulation) and we will collect information regarding safety for both women and babies.

7 Trial design

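### Section 12.2.4 splits the only planned subgroup at <=6/>6 cm, but the objective, the rationale and the minimisation split it at <6/>=6 cm

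*Combined protocol and SAP*

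**What the plan says.** Section 12.2.4 allows one subgroup factor: "Subgroup analyses will be limited to degree of cervical dilation at recruitment (<=6m/>6cm". The first unit is printed as m rather than cm. The section adds: "The results of subgroup analyses will be treated with caution and used for the purposes of hypothesis generation only".

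The other places that define the split are:

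- Section 6.3, repeated in the trial summary in section 1: "To explore any variation in effect in women randomised with cervical dilation <6cms and >=6cms".
- Section 5.2, which commits to an a priori "subgroup analysis of women commencing treatment less than 6cm and equal to or more than 6cm". Here the cut is written in words.
- Section 8, in the list of minimisation variables: "degree of cervical dilation in cm (<6/>=6" (the closing bracket is cut off in this quote).

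Section 12.2.1 brings dilation into the primary model without a cut-point: "Centre and degree of dilation at recruitment will be included as covariates". Section 12.2 says outcomes will be adjusted for the minimisation variables. It calls itself a brief outline and leaves the detail to a separate SAP, which is not part of the supplied text.

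**The concern.** The two definitions differ only for a woman at exactly 6 cm, and they send her to opposite groups. Section 12.2.4 is the text an analyst would program from. Three things are at stake.

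1. **The objective.** The subgroup serves a named secondary objective about <6 against >=6 cm. An interaction test at <=6 against >6 cm answers a different question.
2. **The match with the design.** Minimisation works on <6/>=6 cm. If the adjustment covariate is coded as minimised and the interaction term follows 12.2.4, the analysis carries two codings of one factor.
3. **Prespecification.** While the protocol holds two cuts, the choice could be made after results are seen. That weakens the a priori status claimed in 5.2.

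**Working it through.** **Step 1. The definitions side by side**

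| Section | Lower group | Upper group | Woman at exactly 6 cm |
|---|---|---|---|
| 1 and 6.3, secondary objective | <6 | >=6 | upper |
| 5.2, a priori subgroup | <6 | >=6 | upper |
| 8, minimisation | <6 | >=6 | upper |
| 12.2.4, subgroup analysis | <=6 | >6 | lower |
| 12.2.1, covariate | no cut | no cut | not stated |

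Nothing in the supplied text supports the 12.2.4 cut as the trial's own choice.

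**Step 2. Does the sample size depend on the cut?**

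Inputs from 12.1 and 12.2: 32% against 24%, two-sided 0.05, 90% power, with 1:1 allocation from section 8. Using the pooled-variance formula without continuity correction:

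n per arm = [1.960 × √(2 × 0.28 × 0.72) + 1.282 × √(0.32 × 0.68 + 0.24 × 0.76)]² / 0.08² = 660 after rounding up.

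The total is 1,320, as stated. With 750 per arm and 24% against 18%, power is 81.5% against the stated 80%. The dilation cut does not enter either calculation, so correcting it changes neither figure.

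**Step 3. How many women would change group?**

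The documents do not give the share f at exactly 6 cm, nor do they say that dilation is recorded in whole centimetres. With f as an assumption, the number is 1,500 × f:

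| f | Women who change group |
|---|---|
| 5% | 75 |
| 10% | 150 |
| 20% | 300 |
| 30% | 450 |

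**Step 4. What happens to the interaction estimate?**

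This is an illustration only. Every input is assumed: 45% of women below 6 cm, equal baseline caesarean risk, a relative risk (RR) of 0.90 on the low side of a step and 0.65 on the high side. The true ratio of RRs is 0.65/0.90 = 0.72.

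*Case A: women at exactly 6 cm respond like those above 6 cm.* The <6/>=6 cut recovers 0.72. Under the 12.2.4 cut, the RR in the <=6 group is (0.45 × 0.90 + f × 0.65)/(0.45 + f):

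- f = 0.05: 0.875, ratio 0.65/0.875 = 0.74
- f = 0.15: 0.838, ratio 0.78
- f = 0.30: 0.800, ratio 0.81

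*Case B: women at exactly 6 cm respond like those below 6 cm.* The 12.2.4 cut recovers 0.72. Under the <6/>=6 cut, the RR in the >=6 group is (f × 0.90 + (0.55 − f) × 0.65)/0.55:

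- f = 0.05: 0.673, ratio 0.673/0.90 = 0.75
- f = 0.15: 0.718, ratio 0.80
- f = 0.30: 0.786, ratio 0.87

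In each case the cut that misplaces the 6 cm women pulls the ratio towards 1. Which cut that is depends on a response pattern that the documents do not give.

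**Step 5. Scale against precision**

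In case A with a 32% control risk in both groups and N = 1,500, the standard error of the log ratio is about 0.17 with the <6/>=6 cut. It is 0.17-0.20 with the 12.2.4 cut for f of 15-30%. The shift in the log ratio over that range is 0.07-0.12, which is less than one standard error. Interaction power is about 49% with the <6/>=6 cut and 18-31% with the 12.2.4 cut. The test is underpowered either way.

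**The case against.** The strongest reply is that this is a drafting slip of small consequence. The same bracket prints m for cm, which may itself be a text-reading fault. Section 12.2 is an outline, and the separate SAP may already carry the right cut. The results are labelled hypothesis-generating. Primary model, sample size, randomisation and monitoring do not depend on the cut, and no dilation data are lost. All of this stands, and it limits the severity. It does not remove the contradiction, because the protocol would still disagree with itself whatever the SAP says.

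A reader might infer more than the documents support, in four ways:

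- **That the 12.2.4 cut dilutes any true difference.** This holds only if women at exactly 6 cm respond like those above 6 cm. Case B in the working shows the reverse.
- **That women at 6 cm clinically belong in the upper group.** Section 5.2 reports 6 cm as a marker for the start of the active phase, but also an outside statement that "intervention for delayed labour should not start until the cervix is more than 6cms dilated". The case for <6/>=6 rests on the protocol's own chosen subgroup, not on proof of where 6 cm belongs.
- **That the mismatch with the minimisation biases the comparison.** Allocation is still randomised within <=6 and >6 cm, so the comparisons stay unbiased. Only the arm balance designed for the strata is lost, a small matter of precision.
- **That women at 6 cm will certainly be analysed in the wrong group.** That follows only if 12.2.4 is applied literally. Which cut the SAP uses is unknown.

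**Conclusion.** The inconsistency is real: 12.2.4 stands alone against the objective, the rationale and the minimisation. Applied as written, it analyses women at exactly 6 cm in the opposite subgroup from the one the objective and the minimisation stratum assign them to, so the test does not address the stated secondary objective.

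The number affected is 75-450 of 1,500 under an assumed 5-30% at exactly 6 cm. Neither the direction nor the size of the effect on the interaction estimate can be settled from the documents. The ratios in the working rest on assumed shares, assumed RRs, a step change in effect and equal baseline risk. Severity is minor to moderate, and the conclusion rests on reading the sections against each other, not on the illustration.

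**What to change.** Before unblinded analysis:

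1. Change the bracket in 12.2.4 to <6 cm / >=6 cm and add that this is the cut used in the minimisation.
2. Use the same cut for the interaction term in the SAP.
3. In 12.2.1, state how dilation enters the model. If it is a two-level category, use <6/>=6 cm. A finer form of dilation would also be legitimate, provided that it is stated in advance.

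The cost is a line or two of protocol and SAP wording. There is no extra data collection, no change to sample size or power, and no effect on participants.
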